6.7 Study Intervention after the End of the Study

The Sponsor will not provide any additional care to participants after they leave the study because such care would not differ from what is normally expected for patients with NSCLC.

6.8 Special Precautions

The study will be performed at a clinical research site with personnel trained in basic or immediate life support. Equipment and other agents (epinephrine and prednisolone equivalents, etc.) will be available at the site in case of allergic reactions. In case of localized radiation therapy this should be discussed with the Sponsor (or delegate) on a case-by-case basis.

6.9 Management of Specific Adverse Events, Adverse Events of Special Interest or Adverse Drug Reactions

Tepotinib

Specific Adverse Events

Interstitial Lung Disease

Interstitial lung disease or ILD-like adverse reactions have been reported in the clinical study program with tepotinib in patients with NSCLC.

Participants should be monitored for pulmonary symptoms indicative for ILD or ILD-like reactions. Tepotinib should be withheld and participants should be promptly investigated for alternative diagnosis or specific etiology of ILD. Tepotinib must be permanently discontinued if ILD is confirmed and the participant be treated appropriately.

Edema

Edema has been reported frequently in the study program. It is an identified risk for treatment with tepotinib. Other AEs related to fluid retention, such as generalized edema and pleural effusion have been observed. To gain further information to the occurrence and resolution of edema, any AEs of edema, the current edema status or AE resolution is to be specifically documented at each visit.

In the case of edema, please follow the advice provided in Table 3 in Section [6.6](#).

Asymptomatic Pancreatic Enzyme Elevation

If an asymptomatic lipase/amylase elevation of Grade ≥ 3 occurs, the participant will undergo clinical evaluation for the presence of signs and symptoms typical of acute pancreatitis and for

other risk factors for pancreatitis. In addition, a computed tomography (CT) scan and/or magnetic resonance imaging (MRI) of the abdomen will be performed to assess the pancreas. The Sponsor (or delegate) will be notified of the outcome of the CT/MRI. Dosing with study treatment can continue during the evaluation period unless the clinical evaluation indicates pancreatitis. If there is no clinical or radiological evidence of pancreatitis, treatment with tepotinib should be continued, particularly if there is a potentially positive benefit for the individual participant. However, the continuation of study treatment for the participant will be individually discussed with the Investigator on a participant by participant basis.

In case of dose reduction (Section 6.6), the Investigator should notify the Sponsor immediately and each case should be discussed on a case-by-case basis, providing the reason for dose reduction.

For further information on tepotinib please refer to the tepotinib IB.

Adverse Event of Special Interest (AESI)

Adverse events suggestive of drug-induced liver injury including hepatic/liver failure and hepatitis (non-infectious) are considered AEs of special interest (AESIs) and will be reported to the Sponsor (or delegate) in an expedited fashion (refer to Section 8.3).

Osimertinib

For information on osimertinib please refer to the osimertinib prescribing information.

7 Discontinuation of Study Intervention and Participant Discontinuation/Withdrawal

7.1 Discontinuation of Study Intervention

Participants must be discontinued from study intervention when they meet one of the following criteria:

- Pregnancy (Section 8.3.5)
- ILD/pneumonitis
- Objective disease progression as per RECIST Version 1.1 as per Investigator or participant is no longer receiving clinical benefit.

For participants in the randomized part of the study, verification of disease progression by IRC is required. Participants who are randomized to the tepotinib monotherapy will have the opportunity to switch over to the combination of tepotinib plus osimertinib if they experience disease progression according to RECIST Version 1.1 reported by investigator and verified by IRC. Until progression is verified by IRC and the switch over to the combination of tepotinib plus osimertinib takes place, tepotinib monotherapy can be continued, if judged appropriate by the Investigator. However, if disease progression is not verified by IRC, the participant must discontinue study intervention. Participants who permanently discontinue tepotinib monotherapy due to an AE,

withdraw consent, or for any reason other than progressive disease, will not be eligible to switch over to the combination of tepotinib plus osimertinib.

The Investigator must consider discontinuation of study intervention if he/she believes it is in the best interest of the participant or when a participant meets one of the conditions outlined below:

- Abnormal liver function as defined by the occurrence of Hy's law defined as aminotransferases $> 3 \times \text{ULN}$, ALP $< 2 \times \text{ULN}$, total bilirubin $\geq 2 \times \text{ULN}$, with no other reason to account for these abnormalities
- Grade 4 QTcF increase associated with signs and symptoms of serious arrhythmia
- Grade ≥ 3 lipase and/or amylase elevation with signs and symptoms suggestive of pancreatitis or if pancreatitis is confirmed based on clinical or radiological signs.

The Investigator may consider discontinuation of study intervention when a participant has an increase in QTcF interval greater than 500 ms on at least 2 separate ECGs in line with [Table 3](#).

The Schedule of Activities specifies the data to collect at study intervention discontinuation and follow-up, and any additional evaluations that need to be completed. The reason for study intervention discontinuation should be recorded. If the participant discontinues at a scheduled visit, the EoT assessment can be performed on that day.

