If intolerable toxicities are observed and judged by Investigator to be related to either or both components of the study combination intervention, dose reduction of either or both components will be permitted, if criteria for participant withdrawal from study intervention have not been met. Thereby, the Investigator should notify the Sponsor (or delegate) immediately and each case should be discussed including the reason for dose reduction.

In case a dose reduction is necessary, the study intervention will be administered as follows:

If there is a Grade 3 or higher AE related to either or both components of the combination intervention, dose interruption of either or both components will be permitted for up to 3 weeks. If this AE is not recovered to Grade \leq 2 or baseline values after 3 weeks of interruption, the participant may have to permanently discontinue osimertinib, tepotinib, or both drugs. If this AE recovered to Grade \leq 2 or baseline values in less than 3 weeks, continuation of intervention can be restarted at the same dose or at a lower dose of the respective study interventions. In case of osimertinib, a lower dose of 40 mg is available. In case of tepotinib, depending on the RP2D, a reduction to 250 mg or change in dose regimen is possible. The Investigator is also permitted to reduce the dose of osimertinib and tepotinib for AEs that he/she deem related to the intervention

but is also allowed to escalate back again if the clinical condition allows. Immediate notification of the Sponsor (or delegate) is mandatory.

Further guidance on dose modification of osimertinib is given in [Table 3](#), following information as provided in the Tagrisso EU SmPC dated 28 August 2018. Since this table only provides a snapshot of current available knowledge the Investigator is advised to consider any update of osimertinib information given in respective SmPC revisions.

Table 3 **Recommended Dose Modifications for Tepotinib and Osimertinib**

Target organ	Adverse reaction ^a	Dose modification
Pulmonary	ILD/Pneumonitis.	Permanently discontinue osimertinib and tepotinib.
Cardiac	QTc interval greater than 500 ms on at least 2 separate ECGs.	Withhold osimertinib until QTc interval is less than 481 ms or recovery to baseline if baseline QTc is greater than or equal to 481 ms, then resume at the reduced 40 mg dose.
	QTc interval prolongation with signs/symptoms of serious arrhythmia.	Permanently discontinue osimertinib ^b

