	Symptomatic congestive heart failure	Permanently discontinue osimertinib ^b
Body	Edema Grade 1 or 2	Dose level of tepotinib can be maintained
	Edema Grade 3	The dose of tepotinib must be interrupted until edema recovers to ≤ Grade 2 or baseline but for no more than 21 days. After recovery the patient can restart at the same dose or at 250 mg daily. If edema Grade 3 reoccurs the tepotinib dose must be interrupted again until edema recovers to ≤ Grade 2 or baseline but for no more than 21 days. After recovery, tepotinib must then be dose reduced to 250 mg daily (if the previous dose was 500 mg daily). If edema Grade 3 reoccurs at 250 mg dose, tepotinib must be permanently discontinued.
	Generalized edema Grade 4	Permanently discontinue tepotinib
	Pancreas	See detailed instruction in Section 6.8 .
Other	Any other adverse reaction of Grade ≥3	The dose of tepotinib must be interrupted until event resolves to ≤ Grade 2 or baseline but for no more than 21 days. After recovery, tepotinib may be restarted at 1 dose level below: 250 mg daily.

ECG: electrocardiogram; ILD: interstitial lung disease.

a Adverse reactions graded by NCI CTCAE v5.0

b In the case of permanent discontinuation of tepotinib or osimertinib due to toxicity, participants must permanently discontinue study treatment.

Any clinical circumstances leading to dose modifications and which are not covered by above criteria may be grounds for dose reductions or intervention interruptions and should be discussed with the Sponsor on a case-by-case basis.

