8.2.3 Electrocardiograms

- Single 12-lead ECG will be obtained as outlined in the Schedule of Activities using an ECG machine that automatically calculates the heart rate and measures PR, QRS, QT, and QTcF intervals. Participants will rest for 5 minutes in a semi-supine or supine position before the reading is taken. For study discontinuation criteria involving clinically significant QTcF findings, refer to Section 7.1.

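### For participants on osimertinib, QTc prolongation with signs of serious arrhythmia is a permanent stop in Table 3 but is left to investigator judgment in Section 7.1, where the ECG section sends sites

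*Protocol*

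**What the plan says.** Three places in the protocol bear on this event.

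- **Section 6.6, Table 3.** Under the cardiac heading, the row "QTc interval prolongation with signs/symptoms of serious arrhythmia" carries the action of permanently discontinuing osimertinib, with footnote b attached. The footnote reads: "In the case of permanent discontinuation of tepotinib or osimertinib due to toxicity, participants must permanently discontinue study treatment". The table is titled "Recommended Dose Modifications for Tepotinib and Osimertinib". Its osimertinib guidance is introduced as "following information as provided in the Tagrisso EU SmPC dated 28 August 2018".
- **Section 7.1.** A first list gives the criteria for which participants must be discontinued: pregnancy, ILD/pneumonitis, and progression or loss of clinical benefit. A second list opens with "The Investigator must consider discontinuation of study intervention" and contains "Grade 4 QTcF increase associated with signs and symptoms of serious arrhythmia". A third, weaker statement follows: "The Investigator may consider discontinuation of study intervention when a participant has an increase in QTcF interval greater than 500 ms". Only this last item refers to Table 3.
- **Section 8.2.3 (Electrocardiograms).** "For study discontinuation criteria involving clinically significant QTcF findings, refer to Section 7.1".

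**The concern.** An investigator faced with this event can reach two different rules by two legitimate routes. Starting from Table 3, study treatment stops for good. Starting from the ECG section and following its reference to Section 7.1, the decision is one of judgment.

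The event can be life-threatening, and Section 2.3 of the protocol acknowledges that osimertinib may prolong QTc. Discretion also has a practical consequence. The general text of Section 6.6 allows a related Grade 3 or higher adverse event to be managed by interruption of up to 3 weeks, with restart at the same or a lower dose after recovery. An investigator who treats Section 7.1 as governing, and then applies that general text, could give osimertinib again. Table 3 does not allow this.

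There is a smaller consequence for reporting. SAP Section 10.3.1 counts dose modifications that depart from the protocol among important deviations. Whether continuing after this event is a deviation depends on which section is applied.

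**Working it through.** The main check is textual; no plan calculation is in dispute.

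**1. Is it the same event?** Table 3 gives no grade, while Section 7.1 says Grade 4. The DLT definition in Section 4.1 covers any QTcF increase with signs and symptoms of serious arrhythmia and labels it Grade 4. The protocol therefore uses Grade 4 as the label for this event. The two rules cover the same case.

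**2. What does each rule require of a participant on osimertinib?**

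| Place | Osimertinib | All study treatment |
|---|---|---|
| Table 3 with footnote b | Permanent stop | Permanent stop, mandatory |
| Section 7.1 | Stop must be considered | Stop must be considered |
| Section 8.2.3 | Refers to Section 7.1 | Refers to Section 7.1 |

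**3. Does Section 7.1 defer to Table 3?** Only for the separate item on QTcF above 500 ms. The arrhythmia item carries no such reference.

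**4. How does the protocol look when the two are aligned?** ILD/pneumonitis is a permanent stop in Table 3 and is repeated on the mandatory list in Section 7.1. The arrhythmia event has a permanent stop in Table 3 and a mandatory footnote, yet sits one level lower in Section 7.1.

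**5. Who is affected?** The Table 3 action needs osimertinib to act on, so it concerns the combination arm and monotherapy participants after they switch.

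- Lower figure: 80 in the primary analysis set + about 20 positive by blood test only = about 100.
- Upper figure: about 120 enrolled − 12 centrally confirmed monotherapy participants = about 108. This is an upper bound, because locally positive but unconfirmed participants can also be on monotherapy.
- Ceiling if every monotherapy participant switched: about 120.

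**6. How common might it be?** Section 2.3 reports QTc prolongation in 29 first-line osimertinib patients, given as 10%, with one event of Grade 3 or higher. 29/279 = 10.4%, which reproduces the stated 10% with 279 as the denominator. The severe fraction is 1/279 = 0.36% (exact 95% CI 0.01% to 2.0%). This covers any Grade 3 or higher QTc event. The protocol gives no rate for prolongation with serious arrhythmia.

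**The case against.** The strongest reply is that the two rules can be applied together. Section 7.1 covers both arms, and on tepotinib monotherapy an instruction to stop osimertinib has nothing to act on. Table 3 can then be read as the specific rule for osimertinib. Stopping treatment satisfies both sections. The route is also short: Section 7.1 cites Table 3 just below, for the 500 ms item, and the arrhythmia row follows that row in the table. All of this is fair, and it means the protocol does not give opposite orders. A reader might infer that Section 7.1 authorises continuing against Table 3; it does not say so. But it does not require stopping either, and the precedence that would reconcile the two is nowhere stated.

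A second reply is that Section 7.1 is not a complete list. Symptomatic congestive heart failure and Grade 4 generalized edema are permanent stops in Table 3, and corneal ulcer is a stop in Section 8.2.1; none is on the mandatory list. That is true, and absence alone would not make Table 3 optional. Here, however, the event is not absent. It is named and placed at a discretionary level.

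Third, the table's title calls its content recommended. That softens it, but the action is worded as an instruction and footnote b is mandatory.

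Fourth, there are safeguards: immediate Sponsor discussion of safety concerns (Section 8), SAE reporting of clinical Grade 4 events (Appendix 4), and referral to the osimertinib prescribing information (Section 6.9). They lower the risk. None says which rule applies.

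Two stronger readings should be set aside. One is that Section 7.1 is narrower because it is limited to Grade 4; the DLT definition shows it is not. The other is to scale 1/279 to this trial, giving 0.36 expected events in 100 participants and 0.43 in 120, or a 30% to 35% chance of at least one. Those figures describe any severe QTc event in first-line patients. This trial enrols patients who have already benefited from osimertinib, excludes raised QTcF and QT risk factors, and prohibits drugs that prolong QT and cause Torsade de Pointes. The figures should not be used to argue severity.

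**Conclusion.** The point stands as a participant-safety wording conflict. For a participant taking osimertinib, one event has a mandatory permanent stop in Table 3 with footnote b and a discretionary one in Section 7.1. The ECG section directs sites to the discretionary text.

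Its size is about 100 to 108 participants initially assigned to the combination, at most about 120 after switching, and an event expected to be rare at a rate the documents do not give. The head counts assume that planned enrolment is met. The expectation of rarity rests on the single cited severe QTc event, and assumes that first-line experience is at least a rough guide to the combination.

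A reader might infer an effect on the primary endpoint. The documents do not support that, and none is claimed. The case for fixing it is a possibly fatal event, low probability and a very small correction. Because Table 3 is said to follow the osimertinib EU product information, Section 7.1 is the text to bring into line.

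**What to change.** In the next protocol amendment:

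1. In Section 7.1, add to the mandatory list, for participants receiving osimertinib: "QTc interval prolongation with signs/symptoms of serious arrhythmia", with a reference to Table 3.
2. Keep the must-consider QTcF item, and limit it to participants on tepotinib monotherapy.
3. In Section 8.2.3, change the cross-reference so that it names both Section 7.1 and Table 3.

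A general sentence in Section 7.1 stating that the permanent stops in Table 3 also apply would be a useful addition, since it would cover the other Table 3 events as well. On its own it would leave the arrhythmia item at its present discretionary level, so it does not replace the first two changes.

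The cost is two or three lines of wording. No SAP change, new data collection or change in sample size is needed.

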In addition, osimertinib was investigated head-to-head in a randomized Phase III study in first-line NSCLC versus 1st generation EGFR TKIs, ie, gefitinib and erlotinib (FLAURA, [Soria 2018](#)). Osimertinib not only showed superior efficacy but also had a comparable safety profile to the two 1st generation EGFR TKIs, with a smaller number of severe TEAEs, but a slightly higher frequency of cardiovascular events and interstitial lung disease (ILD). As summarized by [Mezquita 2018](#), 279 participants received osimertinib and 55 participants crossed over to osimertinib from the standard EGFR TKI arm. Fewer Grade ≥ 3 AEs (34%) were reported with osimertinib compared with the 1st generation EGFR TKIs (45%), with a similar overall toxicity profile and a lower SAE rate. The most common AEs were diarrhea (58%), rash (58%), and dry skin (36%). QTc prolongation was reported in 10% of participants (n = 29, one Grade ≥ 3) and ILD in 4% (n = 11, six Grade ≥ 3), with no fatal events. In the osimertinib group, 7 of 11 participants recovered from ILD, and the other 4 were recovering. The rate of permanent discontinuation was lower in the

osimertinib group than with the 1st generation EGFR TKIs (13% versus 18%); however, the rate of dose interruption (24% to 25%) and dose reduction (4% to 5%) due to AEs was similar in both groups.

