	1	2	3	4	5	6	7	8	9	10	11	12
De-escalate from 500 mg to 250 mg in case the number of DLTs is \geq	1	1	2	2	2	3	3	3	4	4	4	5
Escalate back from 250 mg to 500 mg in case the number of DLTs is \leq	0	0	0	0	1	1	1	1	2	2	2	2

DLT: Dose limiting toxicity

At least 6 participants on a dose level are regarded as necessary to select a dose for the Phase II part of the study. In the safety run-in part of the study, DLTs are defined as any of the following toxicities and judged by the Investigator and/or the Sponsor to be not attributable to the disease or disease-related processes under investigation:

- Grade 4 neutropenia for more than 7 days
- Grade ≥ 3 febrile neutropenia
- Grade 4 thrombocytopenia or Grade 3 thrombocytopenia with non-traumatic bleeding
- Grade ≥ 3 nausea/vomiting and/or diarrhea that has not improved within 72 hours despite adequate and optimal treatment
- Any other Grade ≥ 3 non-hematological AE, except alopecia or Grade 3 nausea/vomiting and/or diarrhea that has improved within 72 hours with optimal treatment.

A DLT is also defined specifically in case of:

- Occurrence of Hy's law cases (defined as aminotransferases $> 3 \times$ upper limit of normal (ULN), total bilirubin $\geq 2 \times$ ULN, and alkaline phosphatase (ALP) $< 2 \times$ ULN, with no other reason to account for these abnormalities)
- Grade ≥ 3 lipase and/or amylase elevation with signs and symptoms suggestive of pancreatitis or if confirmation of pancreatitis, either based on clinical or radiological signs. An isolated lipase and/or amylase elevation of Grade ≥ 3 without clinical or radiological evidence of pancreatitis will not be defined as DLT
- Any QTcF increase associated with signs and symptoms of serious arrhythmia (Grade 4)
- Interstitial lung disease/pneumonitis

[figure not shown]
All participants enrolled in safety run-in who miss $> 25\%$ of the planned doses within Cycle 1 will be replaced if the dose reduction/interruption was not caused by any safety reasons/DLTs.

b. MAIN TREATMENT

The main treatment part overview is provided in

[Figure 3.](#)

Figure 3 Main Treatment

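### For participants on osimertinib, Table 3 calls for a permanent stop after QTc prolongation with serious arrhythmia, but Section 7.1 asks only that stopping be considered, and it omits symptomatic heart failure

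*Protocol*

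**What the plan says.** Three places in the Protocol bear on this event.

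- **Section 6.6, Table 3.** The cardiac row "QTc interval prolongation with signs/symptoms of serious arrhythmia" has as its action the permanent discontinuation of osimertinib, marked with note b. Note b reads: "In the case of permanent discontinuation of tepotinib or osimertinib due to toxicity, participants must permanently discontinue study treatment". Symptomatic congestive heart failure has the same action and the same marker. ILD/pneumonitis is a permanent stop of both drugs. The table's title calls these modifications recommended, and the text before it presents the osimertinib part as further guidance taken from the product information.
- **Section 7.1.** The mandatory list has three entries: pregnancy, ILD/pneumonitis, and progression or loss of clinical benefit. A second list opens with "The Investigator must consider discontinuation of study intervention if he/she believes it is in the best interest of the participant", or when a listed condition is met. One of those conditions is "Grade 4 QTcF increase associated with signs and symptoms of serious arrhythmia". A separate sentence says that the Investigator may consider stopping for QTcF above 500 ms on at least 2 ECGs. That sentence holds the only reference to Table 3 in 7.1. Heart failure is not mentioned.
- **Section 8.2.3.** "For study discontinuation criteria involving clinically significant QTcF findings, refer to Section 7.1".

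**The concern.** A site that records a serious arrhythmia with a prolonged QTcF and follows the ECG section arrives at 7.1, where stopping is left to judgement. The general text of 6.6 allows a related Grade 3 or higher event that recovers within 3 weeks to be followed by a restart at the same or a lower dose. Read together, these two texts open a route back to osimertinib that Table 3 closes.

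The stake is participant safety in a rare but possibly life-threatening event. There is also a smaller consequence for conduct. SAP 10.3.1 counts dose modifications that depart from the protocol among important deviations. If a site considers stopping and then continues, the documents do not settle whether it has deviated.

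**Working it through.** The plan gives no figure to reproduce here, so the check is mainly a comparison of texts.

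| Event | 6.6 Table 3 | 7.1 |
|---|---|---|
| ILD/pneumonitis | Permanent stop, both drugs | Mandatory list |
| QTc prolongation with serious arrhythmia | Permanent osimertinib stop, note b | Must-consider list, no reference to Table 3 |
| Symptomatic congestive heart failure | Permanent osimertinib stop, note b | Not listed |
| QTc above 500 ms on at least 2 ECGs | Withhold osimertinib, resume at 40 mg | May consider, in line with Table 3 |

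1. **Is it the same event?** Table 3 gives no grade and 7.1 says Grade 4. The DLT list in 4.1 labels a QTcF increase with signs and symptoms of serious arrhythmia as Grade 4, so the two texts describe one event.
2. **How firm is Table 3?** Its title and introduction are advisory. The cell itself is an unqualified instruction, and note b says *must* once either drug has been permanently stopped for toxicity.
3. **Who is affected?** The row concerns osimertinib. It reaches participants on the combination, including those who have switched over. For tepotinib monotherapy before the switch, *must consider* is the only rule and conflicts with nothing.
4. **Does 7.1 follow Table 3 elsewhere?** Yes for ILD/pneumonitis, which is mandatory in both. No for the two cardiac stops. This looks more like an omission than a decision to leave cardiac stops to discretion.
5. **How common is it?** Section 2.3 reports one Grade 3 or higher QTc prolongation among 279 participants on first-line osimertinib: 1/279 = 0.36%, exact (Clopper-Pearson) 95% CI 0.01% to 1.98%. Applied to the 80 combination participants planned for the primary analysis set, 80 × 1/279 = 0.29 events, with limits of 0.01 to 1.6. Serious arrhythmia is at most a subset of these events, and the documents give no count of it. The figure assumes that the rate on osimertinib alone carries over to the combination, for which the documents give no rate.

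**The case against.** **The texts can be followed together.** Section 7.1 covers both arms and sets a floor, while Table 3 is the drug-specific rule. A site that stops under Table 3 breaches nothing in 7.1. That is true, but the reverse fails: a site that deliberates and continues satisfies 7.1 and departs from Table 3.

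**Table 3 is only guidance.** This stands in part, and it is why the point is put as a conflict between two texts and not as the breach of a binding rule. If the table is purely advisory, the protocol has no firm stop for this event, which would also need saying.

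**Section 7.1 is not a complete list.** Section 8.2.1 requires treatment to stop for corneal ulcer, and 7.1 omits that too. An omission alone creates no contradiction. The arrhythmia event is different because 7.1 names it and gives it a weaker rule. Heart failure is an omission only, and it is worth closing in the same edit.

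**Other safeguards exist.** Section 8 requires immediate safety concerns to go to the Sponsor at once, clinical Grade 4 events are reported as SAEs within 24 hours, an IDMC reviews safety, and exclusion criterion 10 removes participants with raised QTcF or QTc risk factors. A reader of 7.1 also meets a pointer to Table 3 shortly after the arrhythmia item. These make unsupervised re-exposure unlikely. None of them says which rule governs.

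**A reader might infer that the edema stops are defective as well,** since marker b is not visible on those rows and the 6.6 text says "the participant may have to permanently discontinue osimertinib, tepotinib, or both drugs" without citing note b. The documents do not support this. Note b names either drug without limit, so it applies with or without a marker; the table was damaged in extraction; and the 6.6 sentence can be followed alongside note b.

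**Conclusion.** The point holds for participants receiving osimertinib. For one serious cardiac event, Table 3 with note b directs a permanent stop of all study treatment, while the section to which sites are sent asks only that stopping be considered. Symptomatic heart failure has the same Table 3 instruction and no entry in 7.1. This is an inconsistency in a safety rule that should be fixed. It affects conduct and not inference.

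Two stronger readings are not supported. A reader might turn the 1 in 279 into a chance of seeing the event: 1 − (1 − 1/279)^80 = 25%. That figure is for any Grade 3 or higher QTc prolongation, not serious arrhythmia, and carrying the confidence limits through gives about 0.7% to 80%, which is too wide to inform anything. A reader might also infer that the protocol permits osimertinib after a serious arrhythmia. It does not say so; it leaves the governing rule unclear.

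The conclusion assumes that the Table 3 cell and note b are meant as instructions, as their wording suggests, and that the Grade 4 label in 4.1 identifies the events in the two sections as the same.

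**What to change.** 1. In the mandatory list of 7.1, add an entry for participants receiving osimertinib: a QTcF increase accompanied by evidence of serious arrhythmia, or symptomatic congestive heart failure, citing Table 3.
2. In the same list, add a general entry: either drug permanently stopped because of toxicity, citing Table 3 note b.
3. Keep the existing QTcF item in the *must consider* list, restricted to tepotinib monotherapy.
4. In 8.2.3, cite Table 3 alongside 7.1.

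The edema rows and the general text of 6.6 need no change. The cost is a few lines in an amendment and slightly less investigator discretion in a rare event. No new data are needed, and no endpoint, estimand or SAP derivation changes.
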